8.3 Data Transformations

Data transformations will not be used with the exception of transformations that are required for calculation of composite measures; any severely skewed variables will be compared between groups using non-parametric quantile regression.

8.4 Multicenter Studies

This is a single centre study.

8.5 Multiple Comparisons and Multiplicity

EME guidance states that 'a clinical study that requires no adjustment of the type I error is one that consists of two treatment groups, that uses a single primary variable, and has a confirmatory statistical strategy that pre-specifies just one single null hypothesis relating to the primary variable and no interim analysis.' On this basis, the GOLMePsA trial requires no adjustment.

8.6 Planned Subgroups, Interactions, and Covariates

All analyses will control for the stratification factor and baseline values of the outcome. Where the aim is to relate clinical or imaging responses to baseline joint counts or to symptom duration, these variables will be added to the relevant models as covariates after the initial estimate of the treatment effect has been obtained; interactions between each variable and treatment will be assessed and will be considered substantive if found to be significant at the 10% level. Planned exploratory subgroup analyses will investigate differences in treatment response at week 24

according to oligo/polyarthritis status, symptom duration at baseline. The total amount of steroids received by week 12, as a post-randomisation variable, will not be adjusted for in the analysis but will instead be compared between groups.

8.7 Derived and Computed Variables

The following derived and computed variables have been initially identified. It is expected that additional variables will be required. The SAP will not be amended for additional variables that are not related to the primary target or key secondary target variables. Any additional derived or computed variables will be identified and documented in the Stata programs that create analysis files.

Table 1: Derived and computed variables

Variable Name	Description	Valid Values (Ranges)	Computation Methods, Notes or Equations
AGE at baseline	Subject age in years	18-100	=Truncate[number of days between DateOfBirth and DateOfBaseline/365.25] (0 d.p.)
BMI	Body Mass Index	10 to 60	=[Weight (Kg)/Height (m ²)]
PASDAS	Primary endpoint: Psoriatic arthritis disease activity score	0 to 10	((0.18 x vPhysician global VAS) + (0.159 x vPatient global VAS) – (0.253 x vSF36-PCS) + (0.101 x LN (66 swollen joint count + 1)) + (0.048 x LN (68 tender joint count + 1)) + (0.23 x LN (Leeds Enthesitis Count + 1)) + (0.37 x LN (Tender dactylitis count + 1)) + (0.102 x LN (CRP + 1)) + 2)*1.5 See section 15 for details of SF36 PCS calculation
BASDAI	Bath Ankylosing Spondylitis Disease Activity Index	0 to 10	BASDAI=((sum Q1:Q4)+((Q5+Q6)/2))/5
Enthesitis score	Leeds Enthesitis Index	0 to 6	Each of six sites scored (0=absent, 1=present) for enthesitis: medial femoral condyle (2), Achilles tendon (2), plantar fascia insertion (2)
Dactylitis score	Leeds Dactylitis Index	0 to approx. 400	Once the presence of dactylitis is established in each digit, the ratio of the circumference of the affected digit to the circumference of the digit on the opposite hand or foot is measured. If the contralateral digit is also affected then the sex-specific standard reference value corresponding to the digit is used instead. The digit result is then obtained by subtracting 1 from the ratio, multiplying by 100, then multiplying the result by the tenderness score for that digit. The results of each digit are then added to produce a total score
PASI score	Psoriasis area and severity index	0 to 72	Each of four body areas (head & neck, upper limbs, trunk, lower limbs) is scored 0-4 (absent-very severe) for severity of erythema, induration and desquamation. The three scores are summed for each region, then multiplied by the surface area of each region (0.1, 0.2, 0.3 & 0.4 respectively). Each region is also scored for area of psoriasis from 0 (nil) to 6 (90-100%). The severity score is multiplied by the area score and these subtotals are added across the four regions.
mNAPSI score	Modified Nail Psoriasis Severity Index	0 to 140	Each fingernail is scored for the presence and the severity of pitting, onycholysis and nail plate crumbling (score 0-3) and the presence or absence of splinter haemorrhages, leukonychia, red

Variable Name	Description	Valid Values (Ranges)	Computation Methods, Notes or Equations
			spots in the lunula, oil spot dischromia and nail bed hyperkeratosis (score 1 for each if present). This gives a total possible score of 140.
CPDAI score	Composite psoriatic disease activity index	0 to 15	See Table 2 (below) for calculation of CPDAI including the spine
DLQI	Dermatology life quality index	0 to 30	Total of 10 questions across 6 domains scored 0 to 3
HAQ	Health assessment questionnaire disability index	0 to 3	Mean of 8 domains each scored 0-3; within each domain the maximum score is taken. If this is <2 and the patient has reports requiring help or devices for that domain, score for that domain is increased to 2.
ASQoL	Ankylosing spondylitis quality of life scale	0 to 18	Total of 18 responses (0 "No" or 1 "Yes")
SF36-PCS	Short form 36 physical component score	0 to 100	Scoring of SF36 is complex; see section 15 for syntax which corresponds to command: sf36, natver(US) stub(SF)
SF36-MCS	Short form 36 physical component score	0 to 100	Scoring of SF36 is complex; see section 15 for syntax which corresponds to command: sf36, natver(US) stub(SF)
MDA	Minimal disease activity	0 (No) to 1 (Yes)	At least 5 of the 7 following criteria: Tender joint count (/68) \leq 1 Swollen joint count (/66) \leq 1 PASI \leq 1 or BSA \leq 3 Patient pain VAS \leq 15 Patient global disease activity VAS \leq 20 HAQ \leq 0.5 Enthesitis count \leq 1.
PsARCResponse	Psoriatic arthritis response criteria	0 (No) to 1 (Yes)	Overall response is defined by improvement from baseline assessment in 2 of 4 criteria, 1 of which must be a joint count; there must not be worsening in any of the 4 criteria: 1. At least 30% reduction in tender joint grade (total of 68 joints graded 0-3) 2. At least 30% reduction in swollen joint grade (total of 66 joints graded 0-3) 3. At least a 1 point reduction in physician's assessment of articular disease (1-5 Likert scale) 4. At least a 1 point reduction in patient's assessment of articular disease (1-5 Likert scale)
PsARCResponseSens	Psoriatic arthritis response criteria	0 (No) to 1 (Yes)	Overall response is defined by improvement from baseline assessment in 2 of 4 criteria, 1 of which must be a joint count; there must not be worsening in any of the 4 criteria: 1. At least 30% reduction in tender joint grade (total of 78 joints graded 0-3) 2. At least 30% reduction in swollen joint grade (total of 76 joints graded 0-3)

Variable Name	Description	Valid Values (Ranges)	Computation Methods, Notes or Equations
			3. At least a 1 point reduction in physician's assessment of articular disease (1-5 Likert scale) 4. At least a 1 point reduction in patient's assessment of articular disease (1-5 Likert scale)
ACR20/50/70	American college of rheumatology responder index 20 / 50 / 70	0 (No) to 1 (Yes)	The patient must have: ≥20/50/70% improvement in both TJC (68 joints count: as in appendix 8, minus CMC and DIP of the feet) and SJC (66 joints count: as in appendix 8, minus CMC and DIP of the feet) and ≥20/50/70% improvement in at least 3 of the following 5 ACR Core set criteria: 1. Patient's Assessment of Pain Visual Analogue Scale (VAS) 2. Patient's Global Assessment of Disease Activity VAS 3. Physician's Global Assessment of Disease Activity VAS 4. Patient's Assessment of Physical Function as measured by the HAQ-DI 5. Acute phase reactant as measured by CRP
PASI75	PASI 75% response	0 (No) to 1 (Yes)	Patients achieving PASI 75 are defined as having an improvement of at least 75% in the PASI compared to baseline.
US_TotalGS	US total grey scale scores across all common joints	0 to 72	Total of GS scores (0-3) for 24 joints: bilateral wrists, MCPs 2&3, PIPs 2&3, knees, MTPs 1-5, ankle
US_TotalGS_Subset	US total grey scale scores across OMERACT list of joints	0-144	Total of GS scores (0-3) for 48 joints: bilateral wrists, MCP1-5, PIP1-5, DIP2-5, knees, MTP1-5, tibiotalar, talonavicular and subtalar
US_TotalPD	US total power Doppler scores across all common joints	0-72	Total of PD scores (0-3) for 24 joints: bilateral wrists, MCPs 2&3, PIPs 2&3, knees, MTPs 1-5, ankle
US_TotalPD_Subset	US total power Doppler scores across OMERACT list of joints	0-144	Total of PD scores (0-3) for 48 joints: bilateral wrists, MCP1-5, PIP1-5, DIP2-5, knees, MTP1-5, tibiotalar, talonavicular and subtalar
US_GLOESS	US total PDUS scores across all common joints	0-72	Total of PDUS scores (0-3) for 24 joints: bilateral wrists, MCPs 2&3, PIPs 2&3, knees, MTPs 1-5, ankle

Variable Name	Description	Valid Values (Ranges)	Computation Methods, Notes or Equations
US_GLOESS_Subset	US total PDUS scores across OMERACT list of joints	0-144	Total of PDUS scores (0-3) for 48 joints: bilateral wrists, MCP1-5, PIP1-5, DIP2-5, knees, MTP1-5, tibiotalar, talonavicular and subtalar
US_JointRemission	US number of common joints with GS>1 & PD>0 =0 (Y/N)	0-24	Count of joints with GS>1 or PD>0 in 24 joints: bilateral wrists, MCPs 2&3, PIPs 2&3, knees, MTPs 1-5, ankle = 0 (1 if yes, 0 if no)
US_JointRemission_Subset	US number of joints in OMERACT list with GS>1 & PD>0=0 (Y/N)	0-48	Count of joints with GS>1 or PD>0 in 48 joints: bilateral wrists, MCP1-5, PIP1-5, DIP2-5, 8 knee, MTP1-5, tibiotalar, talonavicular and subtalar = 0 (1 if yes, 0 if no)
US_NenthGS	US number of common entheses with GS abnormalities	0-10	Count of GS=1 for 10 entheses: Bilateral quadriceps insertion, patellar ligament proximal insertion, patellar ligament distal insertion, Achilles tendon, plantar fascia
US_NenthGS_Subset	US number of entheses in OMERACT list with GS abnormalities	0-12	Count of GS=1 for 12 entheses: Bilateral lateral epicondyle, quadriceps insertion, patellar ligament proximal insertion, patellar ligament distal insertion, Achilles tendon, plantar fascia
US_TotalEnthPD	US total power Doppler score across common entheses	0-30	Total of PD scores (0-3) for 10 entheses: Bilateral quadriceps insertion, patellar ligament proximal insertion, patellar ligament distal insertion, Achilles tendon, plantar fascia
US_TotalEnthPD_Subset	US total power Doppler score across OMERACT list of entheses	0-36	Total of PD scores (0-3) for 12 entheses: Bilateral lateral epicondyle, quadriceps insertion, patellar ligament proximal insertion, patellar ligament distal insertion, Achilles tendon, plantar fascia
US_EnthRemission	US number of common entheses with GS>1 & PD>0=0 (Y/N)	0-10	Count of entheses with GS>1 or PD>0 in 10 entheses: bilateral quadriceps insertion, patellar ligament proximal insertion, patellar ligament distal insertion, Achilles tendon, plantar fascia=0 (1 if yes, 0 if no).
US_EnthRemission_Subset	US number of entheses in OMERACT list with GS>1 & PD>0=0 (Y/N)	0-1	Count of entheses with GS>1 or PD>0 in 12 entheses: bilateral lateral epicondyle, quadriceps insertion, patellar ligament proximal insertion, patellar ligament distal insertion, Achilles tendon, plantar fascia=0 (1 if yes, 0 if no).

Variable Name	Description	Valid Values (Ranges)	Computation Methods, Notes or Equations
US_NenthCalc	US number of common entheses with calcification	0-10	Count of calcification=1 for 10 entheses: bilateral quadriceps insertion, patellar ligament proximal insertion, patellar ligament distal insertion, Achilles tendon, plantar fascia
US_NenthEnth	US number of common entheses with enthesophytes	0-10	Count of enthesophyte=1 for 10 entheses: bilateral quadriceps insertion, patellar ligament proximal insertion, patellar ligament distal insertion, Achilles tendon, plantar fascia
US_EnthThick	US total thickness score across common entheses: see table 3	0-30	Total of thickness scores (0-3) for 10 entheses: bilateral quadriceps insertion, patellar ligament proximal insertion, patellar ligament distal insertion, Achilles tendon, plantar fascia
US_EnthThick_Subset	US total thickness score across OMERACT list of entheses: see table 3	0-36	Total of thickness scores (0-3) for 12 entheses: bilateral lateral epicondyle, quadriceps insertion, patellar ligament proximal insertion, patellar ligament distal insertion, Achilles tendon, plantar fascia
US_EnthEro	US total erosion score across common entheses	0-30	Total of erosion scores (0-3) for 10 entheses: bilateral quadriceps insertion, patellar ligament proximal insertion, patellar ligament distal insertion, Achilles tendon, plantar fascia
US_EnthEro_Subset	US total erosion score across OMERACT list of entheses	0-36	Total of erosion scores (0-3) for 12 entheses: bilateral lateral epicondyle, quadriceps insertion, patellar ligament proximal insertion, patellar ligament distal insertion, Achilles tendon, plantar fascia
US_EnthInf	US total enthesis inflammation score across common entheses	0-70	=US_NenthGS+ US_TotalEnthPD +US_EnthThick
US_EnthInf_Subset	US total enthesis inflammation score across OMERACT list of entheses	0-84	=US_NenthGS_Subset+ US_TotalEnthPD_Subset+US_EnthThick_Subset
US_EnthChron	US total enthesis chronicity score across common entheses	0-50	=US_NenthCalc+US_EnthEro+US_NenthEnth

Variable Name	Description	Valid Values (Ranges)	Computation Methods, Notes or Equations
US_EnthChron	US total enthesis chronicity score across common entheses	0-60	=US_NenthCalc_Subset+US_EnthEro_Subset+US_NenthEnth_Subset
US_Remission	US remission in common joints	0 (No) to 1 (Yes)	=US_JointRemission==1 & US_EnthRemission==1 if US_JointRemission<. & US_EnthRemission<. (Equates to all common joints and entheses scoring GS<2 and PD==0)
US_Remission_Subset	US remission in OMERACT joint list	0 (No) to 1 (Yes)	=US_JointRemission_Subset==1 & US_EnthRemission_Subset==1 if US_JointRemission_Subset<. & US_EnthRemission_Subset<. (Equates to all scanned joints and entheses scoring GS<2 and PD==0)
US_JointRemissionSens	US remission in common joints (alternative definition)	0 (No) to 1 (Yes)	Count of joints with GS>2 or PD>0 in 24 joints: bilateral wrists, MCPs 2&3, PIPs 2&3, knees, MTPs 1-5, ankle = 0 (1 if yes, 0 if no)
US_EnthRemissionSens	US remission in common entheses (alternative definition)	0 (No) to 1 (Yes)	Count of entheses with GS>0 or PD>0 in 10 entheses: bilateral quadriceps insertion, patellar ligament proximal insertion, patellar ligament distal insertion, Achilles tendon, plantar fascia=0 (1 if yes, 0 if no).
US_ImagingRemissionSens1	US remission (alternative definition 1)	0 (No) to 1 (Yes)	=0 if US_EnthRemissionSens==0 or US_JointRemissionSens==0 =1 if US_EnthRemissionSens==1 & US_JointRemissionSens==1
US_ImagingRemissionSens2	US remission (alternative definition 2)	0 (No) to 1 (Yes)	=0 if US_EnthRemission==0 or US_JointRemissionSens==0 =1 if US_EnthRemission==1 & US_JointRemissionSens==1
US_ImagingRemissionSens3	US remission (alternative definition 3)	0 (No) to 1 (Yes)	=0 if US_EnthRemissionSens==0 or US_JointRemission==0 =1 if US_EnthRemissionSens==1 & US_JointRemission==1
PASDASVLOW	PASDAS very low disease activity	0 (No) to 1 (Yes)	=0 if PASDAS≥1.9 =1 if PASDAS<1.9

Variable Name	Description	Valid Values (Ranges)	Computation Methods, Notes or Equations
PASDASRespM ODGOOD	PASDAS moderate or good response	0 (No) to 1 (Yes)	=0 if improvement≤0.8 or (PASDAS≥5.4 & improvement≤1.6) =1 if (PASDAS≤3.2 & improvement>1.6) or (PASDAS≤3.2 & improvement≤1.6 & improvement>0.8) (PASDAS>3.2 & PASDAS<5.4 & improvement>0.8) (PASDAS≥5.4 & improvement>1.6)
PASDASMCVI mp	PASDAS meaningful change value for improvement achieved	0 (No) to 1 (Yes)	=0 if improvement ≤1.29 =1 if improvement >1.29

Table 2: CPDAI calculation

CPDAI domain	Not involved (0)	Mild (1)	Moderate (2)	Severe (3)
Peripheral arthritis	SJC66=0 & TJC68=0	≤4 Joints (swollen or tender); normal function (HAQ <0.5)*	≤4 Joints but function impaired; or > 4 joints, normal function	>4 Joints and function impaired
Skin disease	'Does the patient currently have skin psoriasis'=No	PASI ≤10 and DLQI ≤10	PASI ≤10 but DLQI >10; or PASI >10 but DLQI ≤10	PASI >10 and DLQI >10
Enthesitis	0 sites involved	≤3 Sites; normal function (HAQ <0.5)*	≤3 Sites but function impaired; or >3 sites but normal function	>3 Sites and function impaired
Dactylitis	0 digits affected	≤3 Digits; normal function (HAQ <0.5)*	≤3 Digits but function impaired; or >3 digits but normal function	>3 Digits and has function impaired
Spinal disease	**	BASDAI <4; normal function (ASQoL <6)	BASDAI ≥4 but normal function; BASDAI <4 but function impaired	BASDAI ≥4 and function impaired

*Health assessment questionnaire (HAQ) only counted if clinical involvement of domain (joint/enthesis/dactylitis) present **Lack of axial involvement

determined according to the Calin inflammatory back pain criteria i.e. <4 of the following satisfied: Back pain onset at age 40 or less; Back pain duration (> 3 months); Back pain onset insidious; Morning stiffness in back; Back pain improves with exercise

Table 3: Thresholds for US enthesal thickening scores

Enthesis	Thickness	Score
Elbow – lateral epicondyle	<5.9mm	0
	≥5.9mm & <6.9mm	1
	≥6.9mm & <7.9mm	2
	≥7.9mm	3
Knee – quadriceps insertion	<7.1mm	0
	≥7.1mm & <8.1mm	1
	≥8.1mm & <9.1mm	2
	≥9.1mm	3
Knee – proximal patellar ligament insertion	<5.0mm	0
	≥5.0mm & <6.0mm	1
	≥6.0mm & <7.0mm	2
	≥7.0mm	3
Knee – distal patellar ligament insertion	<5.0mm	0
	≥5.0mm & <6.0mm	1
	≥6.0mm & <7.0mm	2
	≥7.0mm	3
Ankle – Achilles tendon	<6.29mm	0
	≥6.29mm & <7.29mm	1
	≥7.29mm & <8.29mm	2
	≥8.29mm	3
Foot – plantar fascia	<5.4mm	0
	≥5.4mm & <6.4mm	1
	≥6.4mm & <7.4mm	2
	≥7.4mm	3

9. STUDY SUBJECTS

9.1 Disposition of Subjects and Withdrawals

All subjects who provide informed consent will be accounted for in this study. The frequency and percent of subjects in each population, study withdrawals, subgroups, and major protocol violations will also be presented. The following will be presented:

- Total number of subjects screened (=subjects who gave informed consent)
- Number of randomized subjects.
- Number of randomized subjects who completed the study in each treatment group.
- Number of subjects who discontinued after randomization, grouped by treatment and main reason.
- Number of enrolled/screened, randomized, and analysis populations.

9.2 Protocol Violations and Deviations

The following will be considered major protocol violations and patients meeting any of these criteria will be excluded from the per protocol set. Decisions as to which patients meet these criteria will be made during a blind data review prior to final analysis.

- Patients receiving prohibited prior and/or concomitant medications
- Patients not meeting the following inclusion / meeting exclusion criteria (i.e. those included in error)
 - Inclusion:
 - Subjects with a diagnosis of psoriatic arthritis as per the Classification for Psoriatic Arthritis (CASPAR) criteria confirmed up to 24 months prior to screening.
 - Subjects with active PsA defined as the presence of at least 3/78 tender and at least 3/76 swollen joints or 2 swollen and 2 tender joints plus one affected entheseal site (Achilles tendon and/or plantar fascia) at baseline.
 - Subjects who are treatment naïve to DMARDs.
 - Exclusion:
 - Received previous treatment with any DMARDs at therapeutic dose.
 - Received previous treatment with golimumab or other tumour necrosis factor inhibitor (TNFi) or other biologic drugs.
 - Any chronic inflammatory arthritis diagnosed before 16 years old.

- Patients who have received any systemic/intra-articular corticosteroids within 4 weeks prior to screening. Topical preparations with steroids for cutaneous use, or inhalers for the treatment of asthma are not considered systemic/intra-articular corticosteroids.
- Patients who missed >20% or 2 or more consecutive doses of golimumab
- Patients whose methotrexate treatment was paused for >28 days
- Patients who did not receive the study treatment to which they were randomised (including patients who did not receive steroid bolus at baseline)
- Patients in whom more than one study visit (up to week 24) was outside the 7 day window
- Patients who withdrew from study treatment for any reason
- Patients without primary endpoint data available

The number of study subjects with each violation will be presented in the CTR.

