## STUDY DESIGN

### 5.1 Study description

GOLMEPsA is an investigator initiated, randomised, double-blind, placebo-controlled, two-armed, parallel-group, single-centre imaging study. Patients with the following criteria will be recruited:

- Treatment-naïve PsA patients classified according to CASPAR criteria (33)
- Up to 24 month diagnosis
- At least  $\geq 3$  swollen and 3 tender joints or 2 swollen and 2 tender joints and one tender enthesis.

The trial will start with a four-week screening phase, and informed consent will be obtained at the screening visit. A (revised) total of 84 patients will be randomised on a 1:1 basis to receive one of the following:

**Treatment Arm 1 (Group A):** Immediate golimumab (50 mg SC four weekly) and MTX (starting at 15 mg weekly with rapid escalation up to 25 mg over 4 weeks) combination therapy administered for a total duration of 24 weeks.

**Treatment Arm 2 (Group B):** MTX monotherapy (starting at 15 mg weekly with rapid escalation up to 25 mg over 4 weeks) plus placebo SC injections four weekly for 24 weeks.

Both treatment arms will receive a “bolus” dose of methylprednisolone (120mg IM or equivalent amount intra-articularly in case of oligoarticular,  $\leq 4$  swollen joints, presentation) with the aim to achieve rapid ablation of inflammation at baseline. In addition, both treatment arms will adopt a “treat-to-target” (TT) algorithm (see Schematic Diagram) involving further corticosteroid injections (intra-muscular or intra-articular) if not achieving a PsARC response at weeks 8 and 12 (secondary endpoint). Steroid amount given between both visits will not exceed a maximum amount of 120mg methylprednisolone per patient.

No further steroids will be allowed beyond week 12. Any patients showing an unacceptable degree of disease activity (as judged by the study clinician by clinical assessment in conjunction with PsARC) beyond this point and before the week 24 assessment will cease to follow the study treatment protocol (withdrawal) and will be treated as deemed necessary by the study physician according to clinical protocols and NICE guidelines. In these cases, subjects in the subset in whom WB-MRI was to be collected will undergo WB-MRI as per exploratory objective (see Week X ‘withdrawal visit’, summary schedule of study assessments [section 8.6](#)) and will continue to be observed for the rest of the study duration.

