### 7.3 Non-Investigational Medicinal Product (NIMPs)

Within the trial treatment intervention, the following are classed as Non-Investigational Medicinal Product (NIMPs):

- **Methotrexate**

Methotrexate will be administered orally in both treatment arms at a starting dose of 15mg weekly. If tolerated, it will be increased to 20mg and 25mg weekly at weeks 2 and 4 respectively in both treatment arms.

Subcutaneous MTX may be administered if intolerance to oral MTX is observed.

MTX will be prescribed by the research team and supplied by the hospital pharmacy.

- **Corticosteroids: methylprednisolone**

Both groups will receive corticosteroids at baseline up to a dose of 120 mg methylprednisolone (unless contraindicated or not tolerated). This will be performed either as a stat bolus intra-muscular injection (if  $\geq 4$  swollen joints) or as intra-articular injections (to a maximum of 4 joints injected per visit; 20-80mg per joint with the remainder, if appropriate, given as an intra-muscular injection). The steroid dose administered per joint will be as follows: 80 mg for shoulders, knees or hips; 40 mg if ankles, wrists or elbows; 20 mg if small joints of hands or feet.

Oral steroids (regardless of the indication) are not allowed until week 24. Failure to comply will result in withdrawal from trial medication ([section 7.10](#)). The use of other forms of steroids until week 24 is restricted (as mentioned in exclusion criteria 17, [section 6.3.3](#) of this protocol).

After the completion of trial-related procedures pertaining to week 24, any form of steroid is allowed in accordance to indication and national/local guidance.

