## **11.9 Determination of sample size and randomization method**

Using in-house unpublished data we estimated the minimum clinically important difference to be 0.7 units on the PASDAS; this is similar to a published value for smallest detectable difference of 0.8 units (11). We will aim to detect a difference of at least 1 unit between the treatment arms in this study. The standard deviation of PASDAS in the TICOPA MTX rapid escalation arm (56, 57) at 24 weeks (restricted to patients who remained on methotrexate throughout) was 1.57. Assuming  $\delta=1$ ,  $\sigma=1.57$ , at alpha=0.05 and 1-Beta=0.8 this would require 78 patients. Originally the sample size for the trial was adjusted to account for 10% drop-out, requiring a total of 88 (44 per group). However, because recruitment had been slower than anticipated, in part due to the SARS-CoV-2 pandemic, drop-out was reassessed once 76 participants had the opportunity to reach the primary endpoint. Only 4 (5%) had withdrawn from follow-up prior to that point. Therefore, the total required sample size was revised down to 84 (42 per group) i.e. allowing for 5% drop-out.

For the whole-body MRI subset, published rules of thumb for pilot studies indicate that between 12 and 30 patients per group should be included. We will aim to continue recruiting patients into the WB-MRI subset until there are at least 30 patients (15 per group) with scans available at both baseline and week 24, at which point WB-MRI will cease to be performed in the remaining patients.

To estimate the ICC between two repeated readings of the PASDAS composite index with a confidence interval of width 0.2, we would need 31 patients assuming the ICC is 0.85. For the patient's global assessment of disease activity VAS, which provides the greatest loading on the PASDAS score, ICC = 0.87(35). We will aim to obtain data from at least 31 patients.

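### Per-protocol membership in SAP 9.2 depends partly on response, so the per-protocol sensitivity estimate is expected to shrink if golimumab works; the missed-dose criterion also names golimumab where it should name the IMP.

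*SAP*

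**What the plan says.** Protocol 11.4 and SAP 7 define the per-protocol set as patients who fulfil the protocol on eligibility, interventions and outcome assessment. SAP 9.2 turns this into a list of major violations, to be judged at a blind data review. Three entries matter here.

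- Treatment withdrawal: "Patients who withdrew from study treatment for any reason".
- Missed doses: "Patients who missed >20% or 2 or more consecutive doses of golimumab".
- Not receiving the allocated treatment, "including patients who did not receive steroid bolus at baseline".

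The protocol deals with the same events as follows.

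- Section 5.1 says that patients with unacceptable disease activity between weeks 12 and 24 "will cease to follow the study treatment protocol (withdrawal) and will be treated as deemed necessary by the study physician". Section 7.10 makes the same step discretionary. Section 8.18 allows a change of therapy for non-responders, who then leave the interventional part of the study.
- Compliance is defined on doses of IMP in protocol 10.3.1 and SAP 10.4, and protocol 7.2 lists placebo with golimumab under IMP.
- Section 7.3 states: "Both groups will receive corticosteroids at baseline up to a dose of 120 mg methylprednisolone (unless contraindicated or not tolerated".

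The primary analysis uses the Full Analysis Set as randomised (SAP 11.1). The per-protocol analysis repeats it as one of several sensitivity analyses (SAP 11.3).

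**The concern.** A patient stopped for poor response is removed because of disease activity measured after randomisation, which is close to the endpoint itself. With a common stopping standard and an effective drug, more of these patients come from the methotrexate-plus-placebo arm. Dropping them takes the worst results mainly out of the control arm and narrows the difference.

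A per-protocol result is usually read as a check on adherence. Here it would be expected to come out smaller than the main result even if every investigator and patient did what the protocol provides for, and a reader could wrongly take that as a sign that the primary finding is fragile.

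The missed-dose entry is a separate fault. Read literally, no placebo patient can meet it, and a blind reviewer cannot tell whether a missed injection was golimumab.

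**Working it through.** **The plan's own figure.** Protocol 11.9 gives a target difference of 1 unit, SD 1.57, and "at alpha=0.05 and 1-Beta=0.8 this would require 78 patients". Per arm: n = 2 × (1.960 + 0.842)² × 1.57² / 1² = 38.7, so 39 per arm and 78 in total. Then 78/0.90 = 86.7 gives 88 and 78/0.95 = 82.1 gives 84 after rounding up to equal arms. The figures reproduce. The documents state no figure for the per-protocol set, so its behaviour has to be illustrated.

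**Selection on response.**

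- From the documents: true week 24 difference δ = 1.0 (control minus golimumab) and SD σ = 1.57.
- Assumed: 10, 20 or 30% of controls stop; one common threshold on week 12 activity in both arms; week 12 effect e of 0.5 to 1.0; week 12 to week 24 correlation r of 0.5 to 0.7; baseline correlations of 0.5 with week 12 and 0.4 with week 24.

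Let c be the standard normal quantile that leaves the stated share of controls above it, c_T = c + e/σ, and λ(x) = φ(x)/Φ(x). The share stopped on golimumab is 1 − Φ(c_T). The unadjusted per-protocol difference is

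D = δ − rσ[λ(c) − λ(c_T)].

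The planned analysis adjusts for baseline PASDAS, which recovers part of the loss:

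D_adj = D + b × 0.5σ[λ(c) − λ(c_T)],

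where b is the pooled within-arm slope of week 24 on baseline among those kept. With k(x) = xλ(x) + λ(x)², each arm's covariance is proportional to 0.4 − 0.5r·k and its variance to 1 − 0.25k.

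Worked example (30% of controls, e = 1.0, r = 0.7):

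- c = 0.524 and λ(c) = 0.497; c_T = 1.161 and λ(c_T) = 0.232; 12% are stopped on golimumab.
- D = 1 − 0.7 × 1.57 × 0.265 = 0.71.
- b = 0.287, so D_adj = 0.71 + 0.287 × 0.785 × 0.265 = 0.77.

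| Controls stopped | Golimumab arm stopped | Unadjusted difference | Baseline-adjusted difference |
|---|---|---|---|
| 10% | 3–5% | 0.86–0.94 | 0.89–0.96 |
| 20% | 7–12% | 0.77–0.91 | 0.82–0.94 |
| 30% | 12–20% | 0.71–0.88 | 0.77–0.92 |

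Simulation agrees to within about 0.01; the lowest value can come out as 0.78. If the arms do not differ at either visit, λ(c) = λ(c_T) and the bias is zero.

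**Missed doses.** Over 24 weeks there are 6 injections, or 7 if the week 24 entry in the protocol 8.6 schedule is counted. One miss is 1/6 = 17% or 1/7 = 14%; two are 33% or 29%. So the 20% limit means two or more misses. Protocol 7.10 requires withdrawal from treatment, in either arm, after two consecutive missed IMP doses, and the withdrawal entry in SAP 9.2 then excludes that patient. Only placebo patients with two or more non-consecutive misses escape.

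With an assumed miss probability p per dose and K injections, their share is the sum over m ≥ 2 of C(K − m + 1, m) pᵐ(1 − p)ᴷ⁻ᵐ:

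- K = 6: 0.4%, 2.1% and 6.9% for p of 2, 5 and 10%.
- K = 7: 0.5%, 3.0% and 9.5%.

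That is about 0.2 to 4 of 42 patients. If the rule were applied to golimumab patients only, dropping a share q whose PASDAS is g units worse moves the estimate by qg/(1 − q) in golimumab's favour. For q of 2–10% and g of 0.5–1.0 this is 0.01–0.11 units.

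**The case against.** **Excluding discontinuers is ordinary practice.** The protocol definition refers to interventions, and 5.1 itself says that these patients cease to follow the treatment protocol. This stands. A reader might infer that SAP 9.2 flatly contradicts protocol 11.4; it does not, and only the label of major violation is awkward. The usual reading does not remove the dependence on response, which argues for an added analysis rather than a replaced definition.

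**The golimumab wording is shorthand.** SAP 10.4 itself moves from IMP to golimumab within one paragraph, and a blind review can in practice only count injections in both arms. This also largely stands. The inference that the set selects on adherence in one arm only is not supported beyond the non-consecutive misses. It remains true that the sentence cannot be applied as written.

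**The model is a proxy.** The stopping rule is clinical judgement together with PsARC, and PASDAS is not calculated at the bedside. The only observed rate, 4 of 76, is withdrawal from follow-up, a different quantity. This stands: the direction is firm if golimumab works, but the size is conditional.

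**The bolus entry shows no bias.** The bolus is planned for both arms at baseline, and nothing in the documents links its omission to arm or outcome. This stands; it is a wording conflict only.

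**Conclusion.** The point holds as a limitation of a sensitivity analysis. If golimumab works, the per-protocol estimate should come out below the main one for reasons unrelated to adherence: about 0.77–0.96 instead of 1.0 after baseline adjustment, if 10–30% of controls stop for inefficacy under the assumptions above.

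A reader might go further and conclude that the per-protocol estimate is biased outright, or that the trial's efficacy claim is affected. The documents do not support that. Stopping rates by arm are not given, this route gives no bias when the arms do not differ and so cannot by itself create a false positive, and success is judged on the Full Analysis Set (SAP 11.1). The missed-dose entry is wrong as worded, but its practical reach is small.

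**What to change.** In SAP 9.2:

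1. Replace golimumab in the missed-dose criterion with *IMP (golimumab or placebo)*.
2. Reconcile the steroid-bolus criterion with the exception in protocol 7.3.
3. Report per-protocol exclusions by arm and reason. SAP 9.1 already tabulates discontinuations by treatment and main reason, so little is added.
4. Keep the existing set and add a clearly labelled per-protocol analysis that retains patients stopped for inefficacy under the protocol. Give them the same week 24 value as in the primary analysis, which under SAP 8.2 is carried forward from the withdrawal visit. State that medication given after that stop does not exclude them; otherwise the prohibited-medication entry could remove the same patients.

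Protocol 5.1 (mandatory wording) and 7.10 (discretionary wording) must be reconciled, so that it is clear which stops fall under the rule.

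The cost is a few wording changes and one more sensitivity analysis. Reasons for withdrawal are already recorded in the eCRF (protocol 6.5). The downside is that the added analysis includes some patients with less than 24 weeks of treatment and moves closer to the Full Analysis Set. Because SAP 4.0 postdates unblinding, it must be reported as post hoc beside the original per-protocol result. The sample size and the primary analysis do not change.
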